- (2) Evaluate whether ACT is an effective therapy for reducing associated symptoms of PTSD including anxiety, depression, emotion regulation difficulties, and substance use in comparison to a presumably inactive computer task in individuals with PTSD.
- (3) Compare the effectiveness of an online version of ACT delivered at a distance compared to in the clinic as well as a presumably inactive computer task for combat veterans with PTSD.

This study will be entered on ClinicalTrials.gov to formally register the project. We will add study number once approved by the registry.

Study Participants

Study 1: Recent combat veterans with symptoms of PTSD.

- We have a goal to recruit 100 veterans and active duty personnel serving in the U.S. Military since March 20, 2003 as potential participants for this aspect of the study.
- This sample will be randomly assigned to one of three study arms:
 - Attention control training at the clinic using faces as stimuli
 - Attention control training at the veteran's home via the internet using faces as stimuli
 - Comparison neutral-neutral task at the clinic using faces as stimuli
- Combat veterans with PTSD will be recruited from the community.
- Advertising on TV, with university veteran groups, with Lutheran Family Services, and from other groups serving veterans.

Study 2: Women exposed to interpersonal violence with symptoms of PTSD.

- Attention control training versus comparison task with a total of 60 women who have been exposed to interpersonal violence.
- We will use the faces version of the task with women.
- Participants will be randomly assigned to study condition.
- For safety, we will only include women who are not living with their abuser.
- We will ask about current safety before every session.
- Recruitment and sessions will occur at the Women's Center for Advancement (WCA) or at Creighton University if community women call to participate.

Measures

Demographics. All participants will answer standard demographic questions including age, gender, years of education, and marital status.

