- *Demographics*
- *Alcohol Use Disorders Identification Test*
- *Beck Anxiety Inventory*
- *Difficulties in Emotion Regulation Scale -16*
- *Drug Abuse Screening Test – 10*
- *Patient Health Questionnaire*

- *PTSD Checklist for DSM-5*
- *Threat-Related Attention Bias and Attention Bias Variability*

Participants who give consent and meet the study inclusion criteria but not exclusion criteria, will be randomly assigned to either attention control training or the comparison task in a double blind fashion. Those participants assigned to the neutral-neutral comparison condition will be given the opportunity to participate in ACT training immediately after completing session 8 if they are interested. They can participate in ACT in the clinic or from home online, so all participants will have an opportunity to receive the target intervention. If individuals participate in ACT after completing their participation in the neutral condition of the trial, we will ask them to complete the PCL-5 to assess PTSD symptoms at the end of their ACT training (either in the clinic or online through Qualtrics, Creighton University's online survey platform).

Sessions 2-7: Participants will complete short appointments for their computer attention training or comparison task session. Ideally participants will complete two training sessions per week, such that their participation from start to finish will complete in one month's time.

- For Study 1 sessions will occur in a private room at the Creighton University Psychology Department or online from the participants' personally selected private space (we are encouraging a quiet room in their home). For those participants completing training online, they will be asked to contact study investigators just before starting the task, to offer a relationship aspect to the online delivery and ensure they are conducting their training in a private setting.
- For Study 2 sessions will occur at the WCA or at Creighton University in a private room.

Session 8: Participants will return for a final appointment following training completion, and be reassessed with the same questionnaires and CAPS interview that were employed during the pretreatment assessment. (See the list below for post-intervention questionnaires.) The demographic, trauma screens, and M.I.N.I will be not readministered.

- *Clinician Administered PTSD Scale for DSM-5* (past week version)
- *Alcohol Use Disorders Identification Test*
- *Beck Anxiety Inventory*

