We will conduct a series of standard analyses. For example, we will calculate summative scores for participant questionnaire responses. In addition, we will conduct Repeated Measures Analyses of Variance, t-tests, correlation, and multiple regression analyses on these summative questionnaire scores as well as on the reaction time and accuracy data that we collect during the treatment trials and the pre- and post-training measures.

Anticipated Risks and Mitigation of Risks

We recognize that participating in the assessments required by the study may cause some psychological discomfort to our participants. As a result we regard this project as

having greater than minimal risk. We expect psychological discomfort when participants talk about their traumatic experiences and symptoms during the structured interview or answer questions about these experiences on questionnaires. Psychological assessments will be conducted by trained mental health professionals who are able to recognize any serious exacerbations of symptoms and provide appropriate immediate interventions and referrals.

Specifically, if participants report significant suicidal or violent intent or significant worsening of their symptoms, referrals will be made to [name], MS LMHP, Director of At Ease with Lutheran Family Services in Bellevue NE for the veterans through their partnership with At Ease USA, and for the women through the partnership that At Ease USA has with the WCA. If such referrals are warranted, participation in the trials will be discontinued.

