Important to consider when evaluating the risk/benefit ratio of this study, the VA/DoD (2010) Clinical Practice Guideline for the Management of Post-Traumatic Stress indicates that the mechanisms of action of current evidence-supported treatments for PTSD involve “repetitive review of traumatic memories and trauma-related situations” (p.43). Clearly the most unpleasant aspects of this project - thinking about their own traumatic experiences and related symptoms during the pre and post assessments are forms of exposure therapy. Such exposure is the active ingredient in our current most effective treatments for PTSD, and is considered standard practice in assessment and intervention for PTSD. We realize we are asking difficult questions, but those questions are being asked by or in the presence of our research staff with expertise and experience with PTSD in a private and comfortable setting. Although the assessments are potentially emotional, we also realize that talking about past traumas and symptoms is considered the gold standard of care for PTSD.

Nothing about the training sessions is expected to be difficult. The computerized attention training tasks are simple, brief, and easy. Those training sessions, and the intervention itself, are not associated with any known or expected risks to participants.

Potential Direct and Societal Benefits

If ACT is effective, participants' psychological symptoms may improve. We should note that ACT was shown to be effective in our previous studies, Badura-Brack, et al. (2015), and Khanna et al. (2015), so we are hopeful that this intervention will be effective again. Those participants who were randomly assigned to the comparison intervention will all be invited to continue on after completing formal participation in the study to complete the ACT training protocol in the clinic or online (whichever they prefer). Therefore all participants will have an opportunity to receive the active intervention within approximately 2 months time from initial study enrollment.

If ACT is shown to be effective, we are prepared to begin offering this very low cost,

easy to administer, and easy to experience intervention as therapy to people with PTSD in the near future. Additionally, if ACT is shown to effective at a distance over the internet, barriers to accessing psychological interventions for PTSD could be significantly reduced, because clients could log on to the website from home.

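### Aim 3 sets home ACT against clinic ACT, but the analysis plan gives no interval estimate, margin or rule for a null result, and at about 33 per arm a non-significant difference cannot be read as similar effect

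*Combined protocol and SAP*

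**What the plan says.** The combined protocol and SAP, under Aims for Clinical Trials, gives as Aim 3 to "Compare the effectiveness of an online version of ACT delivered at a distance compared to in the clinic". The same sentence adds the inactive computer task as a second comparator for veterans.

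Study Participants, Study 1, sets the size: "We have a goal to recruit 100 veterans and active duty personnel serving in the U.S. Military since March 20, 2003 as potential participants". It continues: "This sample will be randomly assigned to one of three study arms". The arms are clinic ACT, home ACT and the neutral-neutral task in the clinic. No allocation ratio is given. The randomisation sentence under Session 1, which covers both studies, describes only two conditions: participants "will be randomly assigned to either attention control training or the comparison task in a double blind fashion".

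Proposed Analyses opens with "We will conduct a series of standard analyses" and then names the methods: "we will conduct Repeated Measures Analyses of Variance, t-tests, correlation, and multiple regression analyses on these summative questionnaire scores", together with the reaction-time and accuracy data. It assigns no method to Aim 3. The document states no significance level, effect size, SD, power, margin or confidence-interval criterion, and does not say how a null home-versus-clinic result would be interpreted.

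Potential Direct and Societal Benefits describes the use of the home arm: "if ACT is shown to effective at a distance over the internet, barriers to accessing psychological interventions for PTSD could be significantly reduced".

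**The concern.** Aim 3 names home versus clinic as a comparison in its own right. Testing home ACT against the inactive task does not answer how much of the clinic benefit survives delivery at a distance. As commonly reported, the listed group comparisons yield a p-value for a difference from zero. When arms are small, a non-significant p-value is compatible with anything from no loss to a large one.

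The sponsor intends to offer ACT as therapy soon if it works, and participants from the comparison arm may already choose clinic or home for their later ACT course. A null result reported as *no difference* could easily be taken as support for treating the two settings alike, and nothing in the plan guards against that.

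**Working it through.** The plan has no figure of its own to reproduce, so every effect-size input below is an assumption and is shown as a range.

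**Inputs**
- Recruitment goal 100 and three arms (Study 1). Assumed equal allocation: 100/3 ≈ 33 per arm.
- Assumed: two-sided 5% test, SD = 1 (standardised), pre-post correlation r = 0.6 where baseline is used.
- Assumed ACT benefit over the inactive task: 0.3, 0.5 and 0.8 SD.
- Sensitivity: 28 per arm (assumed 15% loss, 33 × 0.85) and 25 per arm (if half the sample went to ACT and was then split between settings).

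**Step 1: precision of home minus clinic**

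Half-width = t(0.975, 2n − 2) × k × √(2/n). At n = 33, t = 1.998 and √(2/33) = 0.2462.
- Post-training score alone, k = 1: 1.998 × 0.2462 = 0.49 SD.
- Change score, equivalent to the group-by-time test in a two-occasion repeated-measures ANOVA, k = √(2(1 − 0.6)) = 0.894: 0.44 SD.
- Baseline-adjusted, k = √(1 − 0.36) = 0.8: 0.39 SD.

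The unadjusted half-width is 0.54 SD at 28 per arm and 0.57 SD at 25.

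**Step 2: what a null result would leave open**

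Suppose the observed difference is exactly zero. The interval still reaches a loss of 0.49 SD unadjusted or 0.39 SD adjusted. As a share of the assumed benefit:
- Benefit 0.5 SD: 0.492/0.5 = 98% unadjusted; 0.393/0.5 = 79% adjusted.
- Benefit 0.8 SD: 0.492/0.8 = 61% unadjusted; 0.393/0.8 = 49% adjusted.

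**Step 3: chance of non-significance when home delivery is worse**

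True loss = fraction lost × assumed benefit. Non-centrality = loss / (k × 0.2462), with power from the non-central t distribution on 64 df. Example: benefit 0.5 SD, three quarters lost, loss 0.375, non-centrality 0.375/0.2462 = 1.52, power 0.323, chance of non-significance 68%.

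Three quarters of the benefit lost, n = 33:

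| Assumed benefit | Loss | Unadjusted | Change score, r 0.6 | Baseline-adjusted, r 0.6 |
|---|---|---|---|---|
| 0.3 SD | 0.225 | 85% | 83% | 80% |
| 0.5 SD | 0.375 | 68% | 61% | 53% |
| 0.8 SD | 0.600 | 33% | 24% | 15% |

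Other losses at a benefit of 0.5 SD: half lost, 83% (76% adjusted); all lost, 48% (29% adjusted). With 28 per arm, a three-quarters loss is missed 72% of the time at 0.5 SD and 40% at 0.8 SD, unadjusted; with 25 per arm, 75% and 45%.

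**Step 4: could a margin be met at this size?**

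If home and clinic are truly equal, the chance that the 95% CI excludes a loss of m is about Φ(m/SE − 1.96). For an illustrative m = 0.25 SD this is 17% unadjusted (SE 0.246) and 24% adjusted (SE 0.197). For 80% power at that margin, n per arm = 2k²(1.96 + 0.84)²/m², or 252 unadjusted and 161 adjusted.

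**The case against.** Aim 3 says only *compare*. It includes the inactive task as a comparator, and the benefits section speaks of ACT being effective at a distance, which home against the inactive task can address. Nowhere does the plan say that home will be shown to match or replace the clinic, or that non-significance will be read that way. Multiple regression is on the list and could supply an adjusted estimate with an interval. All of this stands. What it leaves untouched is that the home-versus-clinic contrast is named in the aim and has neither a prescribed estimate nor a reading rule.

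Three stronger readings are tempting, and the documents do not support them:
- *The plan makes a non-inferiority claim it cannot support.* No such claim is made. Similarity is an inference that a reader might draw from a null result.
- *A null result is likely even if home delivery is useless.* At an assumed 0.5 SD benefit and 33 per arm, total loss gives non-significance 48% of the time, or 29% adjusted, so it is not the more likely outcome. A useless home arm should also show no benefit over the inactive task.
- *A null result is likely whenever most of the benefit is lost.* This depends on an effect size that the documents do not give. For a three-quarters loss it holds at 0.3 SD and, less clearly after adjustment, at 0.5 SD; it fails at 0.8 SD.

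**Conclusion.** The point holds as a gap in analysis and interpretation. With about 33 per arm, the home-minus-clinic interval spans roughly ±0.49 SD unadjusted, ±0.44 SD on change scores and ±0.39 SD baseline-adjusted, so a non-significant difference is not evidence of similar effect. That conclusion does not need a small ACT benefit: even at 0.8 SD, an observed difference of zero leaves open a loss of about half the benefit after adjustment. How often a serious loss would be missed does depend on the assumed benefit, from 85% down to 33% unadjusted (80% to 15% adjusted) for a three-quarters loss.

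The figures rest on equal allocation, the full 100 being randomised and analysed, r = 0.6 and a two-sided 5% level, none of which is stated. The 100 is a goal for potential participants, so the arms may be smaller, which would widen the intervals. This is an inexpensive improvement to the plan and does not put Aim 3's comparison with the inactive task in doubt.

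**What to change.** In Proposed Analyses, add a paragraph for Aim 3:
- Analyse home versus clinic ACT as a baseline-adjusted (ANCOVA) difference in the post-training PTSD score, naming the instrument, and report it with its 95% CI.
- Label this an estimation contrast, separate from the test of home ACT against the inactive task.
- State that a non-significant p-value will not be reported as equal or comparable effectiveness.
- Optionally, if the sponsor wants to use the word *comparable*, fix the largest acceptable loss before any outcome analysis, and use the word only if the CI excludes that loss. Otherwise report the result as inconclusive. The timing should be tied to outcome analysis and not to unblinding, because participants and the staff they contact will know who trains at home.

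The cost is wording only: no extra participants, visits or data, since the scores are already collected at Sessions 1 and 8. The downside is that the likely Aim 3 statement becomes less favourable, *inconclusive* in place of *no difference*. A formally powered non-inferiority comparison would be a different trial (161 to 252 per arm at the illustrative 0.25 SD margin) and is not asked for here.

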Participants will be assigned to attention control training or the comparison stimuli computer task in a double-blind randomized control trial design. Both computerized dot probe tasks display two stimuli on a computer screen, one above the other, followed by a small right or left arrow appearing in the location vacated by one of the faces (see figure below). Participants are required to respond as quickly as they can by pressing the indicated right or left arrow on their computer keyboard without compromising accuracy.

In all trials, attention control training will present one neutral and one threatening stimulus on the screen. In most aspects of the study, the stimuli will be pictures of facial expressions. Specifically, in attention training, the participant will view one neutral face and one angry face on the screen at the same time. In the comparison condition, the

stimuli will always be two neutral faces presented before responding to the arrow.

Our investigational intervention = Attention Control Training will consist of:

- 6 sessions lasting approximately 10 minutes each.
- Each session will consist of 128 presentations of pairs of neutral and threatening stimuli, followed by the presentation of a response cue (right or left arrow to be clicked on a computer keyboard).
- Ideally participants will complete 2 sessions per week, allowing them to complete the trial in less than one month's time

Our comparison task will consist of:

- 6 sessions of a presumably inactive neutral-neutral intervention lasting approximately 10 minutes each.
- Each session will consist of 128 presentations of pairs of faces, followed by the presentation of a response cue (right or left arrow to be clicked on a computer keyboard).
- Ideally participants will complete 2 sessions per week, allowing them to complete the trial in less than one month's time.

IMPORTANTLY, after completing this inactive intervention and post assessment, all of these participants whose PTSD symptoms have not improved will be invited to return for a full trial of attention control training as described above to mitigate any concerns about a theoretically inactive intervention.

Aims for Clinical Trials

The major aims of the trials are straightforward:

- (1) Evaluate whether attention control training (ACT) is an effective therapy for reducing PTSD symptoms in combat veterans and/or women who have experienced interpersonal violence in comparison to a presumably inactive computer task.

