Difficulties in Emotion Regulation Scale -16 (DERS-16; Bjureberg et al., 2016). Comprised of 16 items, the DERS-16 provides a brief, yet comprehensive measure of emotion regulation abilities. The DERS-16 assesses five of the original six domains of emotion regulation including, for example, lack of emotional clarity, difficulty controlling impulsive behaviors when distressed, and limited access to emotion regulations strategies perceived as effective. Participants rate items such as "I have difficulty making sense out of my feelings" and "When I am upset, I become out of control" on a 5-point Likert scale (1=*almost never*; 5=*almost always*). The brief measure evidenced strong internal consistency, good test-retest reliability, as well as good convergent and discriminant validity in clinical and community samples. In addition, there were minimal differences in validity between the DERS-16 and the original, 36-item DERS (Bjureberg et al., 2016).

Drug Abuse Screening Test – 10 (DAST-10; Bohn, Babor, & Kranzler, 1991; Skinner, 1982). The DAST-10 is designed to provide a brief, self-report measure of substance abuse in the last 12 months. Specifically, participants are asked to consider their use of drugs such as cannabis, cocaine, hallucinogens, and narcotics, while excluding their use of alcohol and tobacco. Composed of 10-items, participants respond 'yes' or 'no' to questions such as "Have you ever experienced withdrawal symptoms (felt sick) when you stopped taking drugs?" and "Have you neglected your family because of your use of drugs?" DAST-10 scores range from 0 to 10 with higher scores indicative of more severe drug abuse. The DAST is a widely-used measure of substance abuse with sound psychometric properties. The DAST-10, specifically, has shown high internal consistency, adequate test-retest validity, and convergent and divergent validity with appropriate measures (Yudko, Lozhkina, & Fouts, 2007).

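### The DAST-10 looks back 12 months but is repeated about one month after baseline, so it is very insensitive to the fall in drug use that Aim 2 asks about

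*Combined protocol and SAP*

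**What the plan says.** Under Aims for Clinical Trials the protocol writes that "The major aims of the trials are straightforward". Aim 2 is to test whether ACT is effective for "reducing associated symptoms of PTSD including anxiety, depression, emotion regulation difficulties, and substance use", against the inactive task.

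Under Measures, the DAST-10 is described as "designed to provide a brief, self-report measure of substance abuse in the last 12 months". It excludes alcohol and tobacco, has ten yes/no items and is scored 0 to 10. One of the two example items reads "Have you ever experienced withdrawal symptoms (felt sick) when you stopped taking drugs".

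Under Step by Step Procedures, the DAST-10 is in both the Session 1 and the Session 8 lists. At Session 8 participants are to "be reassessed with the same questionnaires and CAPS interview that were employed during the pretreatment assessment". For the CAPS-5 the plan does specify a different look-back at that visit ("past week version", against past month at Session 1). It specifies none for the DAST-10.

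On timing, the Method section describes two sessions a week as ideal, "allowing them to complete the trial in less than one" month. The Sessions 2-7 text says the same, "such that their participation from start to finish will complete in" one month. The follow-up contacts at 6 months and 1 year list general questions and the PCL-5, not the DAST-10. Proposed Analyses lists repeated-measures ANOVA, t-tests, correlation and regression on summed scores, with nothing specific to this scale.

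**The concern.** A change score can show improvement only if the second measurement covers time after the intervention began. Here the second DAST-10 covers almost the same twelve months as the first. Yes/no scoring gives no credit for using less: one qualifying event anywhere in the window keeps the item at *yes*. Randomisation keeps the comparison unbiased but does not help, because both arms carry the same kind of pre-baseline history into the Session 8 score.

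At stake is the drug-use component of Aim 2. No other post-baseline drug-use measure is listed, and no later visit repeats this one. A flat result is therefore likely whether or not ACT changes drug use in people who report problems at entry.

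**Working it through.** The plan gives no power, effect size, significance level or DAST-10 mean or SD, so there is no stated figure to reproduce. Steps 1 and 2 need only the plan's own text. Steps 3 to 5 are models with assumed inputs.

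**Inputs.** Window W = 365 days (Measures, DAST-10). Gap t from Session 1 to Session 8: about one month as planned. Because that timing is only an ideal, I use a range of 21 to 61 days.

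**Step 1. Share of the Session 8 window before baseline, (W − t)/W.**

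| Gap t (days) | Days before baseline | Share |
|---|---|---|
| 21 | 344 | 94.2% |
| 28 | 337 | 92.3% |
| 35 | 330 | 90.4% |
| 61 | 304 | 83.3% |

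**Step 2. Who can change from *yes* to *no*.** Suppose a participant stops completely at Session 1. An item endorsed at baseline can become a truthful *no* only if every qualifying event lay in the oldest t days of the baseline window. If the last event was within W − t days before Session 1 (337 days at t = 28), the answer must still be *yes*.

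**Step 3. How often that happens, assuming a constant event rate L per year.** With f = t/365, the probability that a baseline *yes* becomes *no* under full cessation is e^(−L(1−f)) · (1 − e^(−Lf)) / (1 − e^(−L)). With no change in behaviour it is that value times e^(−Lf). At t = 30:

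| L per year | Full cessation | No change |
|---|---|---|
| 0.5 | 6.5% | 6.2% |
| 1 | 5.0% | 4.6% |
| 2 | 2.8% | 2.4% |
| 4 | 0.7% | 0.5% |

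At these rates, complete cessation shifts the proportion of baseline *yes* answers turning to *no* by at most about 0.4 percentage points.

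**Step 4. Effect on the score, same idea in months.** Let p be the monthly probability of a qualifying event, equal for every item and person, with complete cessation in the ACT arm and no change in the comparison arm. The between-arm difference is 10·p(1−p)^11. At p = 1/12 this is 0.32 of 10 points. It splits into 10·p(1−p)^12 = 0.29 from new *yes* answers prevented and 10·p²(1−p)^11 = 0.03 from improvement in people already at *yes*. The split is a model result: the improvement share equals p by construction.

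**Step 5. Would a one-month form detect more?** Same model, change scores, Welch t-test, two-sided 0.05, 30 per arm (Study 2's 60 women, equal split assumed). The implied baseline mean on the 12-month form is 10·[1 − (1−p)^12]. For the one-month form the difference is 10p.

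Per-item change variances are:
- 12-month form: 2p(1−p)^12 (comparison) and a − a² with a = p(1−p)^11 (ACT).
- One-month form: 2p(1−p) (comparison) and p(1−p) (ACT).

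Multiply by 10 for independent items and by 100 for perfectly correlated items.

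| Baseline mean | Difference, 12-month vs one-month form | Power, independent items | Power, perfectly correlated items |
|---|---|---|---|
| 1.0 | 0.079 vs 0.087 | 14% vs 15% | 6% vs 6% |
| 2.0 | 0.15 vs 0.18 | 23% vs 27% | 7% vs 7% |
| 3.0 | 0.21 vs 0.29 | 30% vs 40% | 7% vs 8% |
| 6.5 (p = 1/12) | 0.32 vs 0.83 | 44% vs 84% | 9% vs 16% |
| 9.3 (p = 0.20) | 0.17 vs 2.00 | 28% vs over 99% | 7% vs 34% |

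The gain is large only where the assumed baseline score is high. At a mean of 1 it is close to nil, because events are then too rare for either form.

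**The case against.** **The scale can still move.** True. New use after Session 1 is fully detectable, so a reader who infers that the DAST-10 cannot differ between arms goes too far. What it barely registers is improvement among people who endorse items at entry.

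**The gain from a shorter window is unproven.** This stands. It is tempting to say that a short form would roughly double power (44% to 84%), but that figure implies a mean baseline score of 6.5 out of 10, and Pre-Screen excludes current substance dependence. The documents give no DAST-10 distribution. A sample with a few frequent users and many non-users would behave differently from the uniform model, and nothing in the documents settles which applies.

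**No conclusion of no effect is planned.** Also true. Proposed Analyses contains no equivalence test, and a non-significant result on any outcome would not by itself show absence of effect. The point particular to the DAST-10 is its low sensitivity to improvement.

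**The item worded *ever* may not be a lifetime item.** A reader might infer that it can never fall. The protocol presents the whole instrument as covering 12 months, so that is only one interpretation of one example.

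**Participants may answer from recent behaviour.** Possibly, but that departs from the instrument as described, and the plan does not provide for it.

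**The AUDIT.** A reader might extend the point to alcohol. The protocol quotes one item about the last year and gives no window for amount and frequency, so no finding follows beyond a check.

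**Conclusion.** The concern holds in this form: as scheduled, the DAST-10 is very insensitive to the improvement Aim 2 names, and a non-significant comparison says little about whether ACT reduces drug use. The size that needs no model is the overlap: about 92% of the Session 8 window precedes baseline at the planned interval, and 83% if the gap stretches to two months. This rests on the stated 12-month window, truthful answers to it, and no unstated change of form at Session 8. The transition rates, score differences and power figures rest on assumed event rates and are illustrations only.

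Severity is minor. One component of one aim is affected. Aim 1 is untouched, and no bias toward either arm is shown.

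**What to change.** 1. Keep the 12-month DAST-10 at Session 1 as a baseline descriptor.
2. At both Session 1 and Session 8, give a form with a short fixed look-back (for example past two weeks or past month), set no longer than the planned interval between those sessions. Name it as the Aim 2 drug-use comparison. A 30-day window would still reach 9 days before baseline for someone who finishes in 21 days; a two-week window would not.
3. Confirm that the form's look-back governs any item worded *ever*.
4. If no short form is added, state in Proposed Analyses that the 12-month DAST-10 comparison supports no conclusion on reduction in drug use.
5. For the AUDIT, check and record each item's look-back before using its change score.

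**Cost.** A ten-item questionnaire and a few minutes at Session 1; at Session 8 it replaces the 12-month form. The short form departs from the validated wording and *yes* answers will be rarer, so it may still have little power if baseline use is low. Step 4 costs one sentence but leaves the drug-use part of Aim 2 unanswered. Repeating the 12-month form at the 1-year follow-up is no substitute, because comparison participants are offered ACT after Session 8.
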